6.8. Handling of Missing Data

6.8.1. Missing Efficacy Endpoints

Missing efficacy endpoints will be imputed for week 12 IGA and lesion count analyses only. Details can be found in Section 8.3.

6.8.2. Missing Start and Stop Dates for Prior and Concomitant Medication

Start date:

- 1. If start date is completely missing, start date will not be imputed.
- 2. If (year is present and month and day are missing) or (year and day are present and month is missing), set month and day to January 1.
- 3. If year and month are present and day is missing, set day to the 1st day of month.

Stop date:

- 1. If end date is completely missing, end date will not be imputed.
- 2. If (year is present and month and day are missing) or (year and day are present and month is missing), set month and day to December 31st.
- 3. If year and month are present and day is missing, set day to the last day of month.

Further details on classifying medications as either prior or concomitant are outlined in the protocol Section 6.6.

6.8.3. Missing Start and Stop Dates for Adverse Events

Start date:

- 1. If start date is completely missing, start date is set to date of first dose.
- 2. If (year is present and month and day are missing) or (year and day are present and month is missing):
 - a. If year = year of first dose, then set month and day to month and day of first dose.
 - b. If year < year of first dose, then set month and day to December 31st.
 - c. If year > year of first dose, then set month and day to January 1st.
- 3. If month and year are present and day is missing:
 - a. If year = year of first dose and
 - i. If month = month of first dose, then set day to day of first dose date.
 - ii. If month < month of first dose, then set day to last day of month.
 - iii. If month > month of first dose, then set day to 1st day of month.

¹ Visit 1 and 2 may have been combined if no washout was required, but should not have been separated by more than 60 days.

- b. If year < year of first dose, then set day to last day of month.
- c. If year > year of first dose, then set day to 1st day of month.

Stop date:

If the outcome of the AE was ongoing or unknown, then the rules outlined below will not be applied.

- 1. If stop date is completely missing, stop date is set to date of study discontinuation.
- 2. If (year is present and month and day are missing) or (year and day are present and month is missing):
 - a. If year = year of study discontinuation, then set month and day to month and day of study discontinuation.
 - b. If year < year of study discontinuation, then set month and day to December 31st.
 - c. If year > year of study discontinuation, then set month and day to December 31st.
- 3. If month and year are present and day is missing:
 - a. If year = year of study discontinuation and
 - i. If month = month of study discontinuation, then set day to day of study discontinuation date.
 - ii. If month < month of study discontinuation, then set day to last day of month.
 - iii. If month > month of study discontinuation, then set day to last day of month.
 - b. If year < year of study discontinuation, then set day to last day of month.
 - c. If year > year of study discontinuation, then set day to last day of month.

7. STUDY POPULATION

7.1. Subjects Disposition

The subject disposition summary will include the number screened, the number of screen failures, the number enrolled, the number in each patient population for analysis, the number who completed the study, the number who discontinued the study and reason for discontinuation from the study. Disposition data will be summarized by treatment and overall.

A by-subject data listing of study completion information including the reason for study discontinuation will be presented. A by-subject listing of inclusion/exclusion criteria not met will also be presented.

7.2. Protocol Deviations

A summary of all protocol deviations by type will be generated. Protocol deviation data will be summarized by treatment and overall. A by-subject data listing of protocol deviations will also be presented.

7.3. Demographic and Baseline Characteristics

The following demographic and baseline characteristics will be summarized by treatment and overall:

- Age (Years)
- Age Group (12 16 Years, 17 64 Years, 65 Years or Older)
- Gender (Male, Female)
- Race (White, Black or African American, Asian, American Indian or Alaskan Native, Native Hawaiian or Other Pacific Islander and Other)
- Ethnicity (Hispanic or Latino, Non-Hispanic or Non-Latino)
- Fitzpatrick Classification Scale (I, II, III, IV, V, VI)
- Investigator's Global Assessment (IGA) at Baseline (0 = Clear, 1 = Almost Clear, 2 = Mild, 3 = Moderate, 4 = Severe)
- Inflammatory Lesion Count
- Non-inflammatory Lesion Count

Age will be computed using date of birth and baseline visit date with details in Section 6.7.1.

The Fitzpatrick skin scale classifies a person's complexion and tolerance of sunlight. It is commonly used by many practitioners to determine how someone will respond or react to facial treatments. The Fitzpatrick skin scale is presented in Table 4 below.

Table 4: Fitzpatrick Classification Scale

Skin Type	Skin Color	Characteristics
I	White; very fair; red or blond hair; blue eyes; freckles	Always burns, never tans
II	White; fair; red or blond hair; blue, hazel, or green eyes	Usually burns, tans with difficulty

Skin Type	Skin Color	Characteristics
III	Cream white; fair with any eye or hair color; very common	Sometimes mild burn, gradually tans
IV	Brown; typical Mediterranean Caucasian skin	Rarely burns, tans with ease
V	Dark Brown; mid-eastern skin types	Very rarely burns, tans very easily
VI	Black	Never burns, tans very easily

7.4. Medical History

Medical history verbatim text will be coded and classified by system organ class (SOC) and preferred term (PT) using the MedDRA (Version 20.0).

Medical history summary tables will use the following algorithms for counting subject histories within the summary tables:

- Any medical history row: Each subject with a medical history is counted only once although he/she may have several medical histories.
- System organ class rows: Each subject is counted only once at each SOC level although he/she may have several different PT events within the same SOC.
- Preferred term rows: Each subject is counted once within each unique PT.

Medical history data will be summarized by treatment and overall. A by-subject data listing of medical history will also be presented.

8. EFFICACY ANALYSES

8.1. Efficacy Assessments

The investigator was responsible for all clinical evaluations, with best attempts made to assign the same evaluator for a subject throughout the study to obtain consistency in grading scores and measurements.

Efficacy assessments were conducted using IGA for overall disease severity and inflammatory and non-inflammatory lesion counts on the face. The IGA was always done prior to lesion counts.

8.1.1. Investigator's Global Assessment (IGA) of the Face

The IGA scale used in the study is a measure of static evaluation of qualitative overall acne severity. IGA is an ordinal scale with five severity grades (reported only in integers, e.g., 0 to 4). Each grade is defined by a distinct and clinically relevant morphologic description to minimize inter-observer variability (Table 5). The grades on the scale have been sufficiently defined to appropriately and unambiguously represent each severity grade on the scale. The investigator was required to perform IGA scoring at each visit. The IGA was always done prior to lesion counts.

Table 5: IGA Scale for Facial Acne Vulgaris

Grade	Description ¹
0	Clear skin with no inflammatory or non-inflammatory lesions
1	Almost clear; rare non-inflammatory lesions with no more than rare papules
2	Mild severity; some non-inflammatory lesions with no more than a few inflammatory lesions (papules/pustules only, no nodular lesions)
3	Moderate severity; up to many non-inflammatory lesions and may have some inflammatory lesions, but no more than one small nodular lesion
4	Severe; up to many non-inflammatory and inflammatory lesions, but no more than a few nodular lesions

¹ Areas other than the face and nose were not included in assessment.

Enrollment of subjects with mild acne (IGA Grade 2) at each site was restricted to no more than 20% of total enrollment at that site; management of this requirement was handled by the IWRS.

8.1.2. Lesion Counts of the Face

Non-inflammatory lesions (closed comedones and open comedones), inflammatory lesions (papules and pustules), and nodulocystic lesions (nodules and cysts) on the face (above the mandibular line), including the nose, were counted and recorded separately at each visit from Screening/Baseline through Week 12. Non-inflammatory lesions of acne are the open (blackheads) or closed (whiteheads) comedones. Closed comedones may be more difficult to detect visually and may require stretching of the skin to aid in visualization. Inflammatory lesions are divided into papules, pustules, and nodules/nodulocystic lesions, depending on the severity and location of the inflammation within the dermis. Nodulocystic lesions will be counted separately from inflammatory lesions of papules and pustules. The papules and pustules have surrounding halos of erythema allowing for their characterization as inflammatory.

Nodules are typically erythematous and often tender and/or painful. Additionally, they are deep- seated in the skin (i.e., centered in the dermis or subcutis). Nodules have been defined as being greater than 5 mm in diameter. The borders of these lesions may be difficult to determine because of the associated

erythema/inflammation. The investigator/evaluator should have used standard, good lighting to visualize lesions and a systematic counting procedure to ensure consistent and accurate counts.

8.1.3. Lesion Counts of the Chest and/or Back (including shoulders)

At selected site(s), for subjects who had acne lesions on their chest and/or back (including shoulders), lesion counts were assessed separately for these areas.

Non-inflammatory lesions (closed comedones and open comedones), inflammatory lesions (papules and pustules), and nodulocystic lesions (nodules and cysts) on the chest and/or back including shoulders (if applicable) were counted and recorded separately at each visit from Baseline through Week 12. Nodulocystic lesions were counted separately from inflammatory lesions of papules and pustules. The back area is from most prominent cervical spinous process superiorly to the superior aspect of iliac crest inferiorly and the shoulder area was also included. The chest area is from the manubrium of the sternum superiorly to the xiphiod process inferiorly. The lesion types were as described above. The investigator/evaluator was to use standard, good lighting to visualize lesions and a systematic counting procedure to ensure consistent and accurate counts.

8.1.4. Cardiff Acne Disability Index (CADI)

The CADI is a short 5 item questionnaire that will be conducted by all subjects at Baseline, Week 4, 8, and 12. The questionnaire rapidly assesses the disability caused by the acne. It consists of 5 questions. The scoring for each question is done from 0 to 3 (a=3, b=2, c=1, d=0). The CADI score is calculated by summing the score of each question resulting in a possible maximum of 15 and a minimum of 0. The higher the score, the more the quality of life is impaired.

The CADI questionnaire is provided in Appendix 2 of the protocol.

8.2. Subgroup Analyses

For the safety and efficacy endpoints the following subgroup analyses will be done:

Table 6: Summary of Subgroup Analyses

Subgroup	Specification Values
Age Group 1	$12 - 16 \text{ Years}, 17 - 64 \text{ Years}, \ge 65 \text{ Years}$
Age Group 2	< Median Age, ≥ Median Age
Gender	Male, Female
Race	White, Black or African American, Asian, Other
Ethnicity	Hispanic or Latino, Not Hispanic or Latino
Fitzpatrick Classification Scales	I-IV, V-VI

For the safety analyses, safety will be summarized for all subgroups except Fitzpatrick Classification Scales. For the efficacy analyses, efficacy will be summarized for all subgroups.

8.3. Analysis of the Efficacy Endpoints

The following efficacy endpoints will be summarized using descriptive statistics for both the ITT and PP populations:

- Proportion of Subjects with IGA Success at Weeks 4, 8 and 12. IGA success is defined as an IGA score of 0 (Clear) or 1 (Almost Clear) with at least a 2-grade reduction from baseline.
- Absolute Change from Baseline in Inflammatory Lesion Counts at Weeks 4, 8 and 12. The following location of lesions will be summarized separately: face and chest/back/shoulders.
- Absolute Change from Baseline in Non-Inflammatory Lesion Counts at Weeks 4, 8 and 12. The following location of lesions will be summarized separately: face and chest/back/shoulders.
- Percent Change from Baseline in Inflammatory Lesion Counts at Weeks 4, 8 and 12. The following location of lesions will be summarized separately: face and chest/back/shoulders.
- Percent Change from Baseline in Non-Inflammatory Lesion Counts at Weeks 4, 8 and 12. The following location of lesions will be summarized separately: face and chest/back/shoulders.
- Change from Baseline to Weeks 4, 8 and 12 in CADI.

For all efficacy endpoints for the ITT and PP populations, data will be summarized at week 4, 8 and 12 with data as is where missing data is not imputed.

Also for missing IGA and lesion counts in the ITT population, data will be summarized at week 12 where the primary handling method for missing data, except for baseline, will be the multiple imputation (MI) approach via regression. In details, the MI regression model will include the following predictors in the model: treatment, age, gender, baseline inflammatory lesion counts, baseline non-inflammatory lesion counts, and the results of the same variable from previous visits. The average score of the MI copies will be used to calculate the summary statistics.

Finally for missing IGA, lesion counts and CADI in the PP population, data will be summarized at week 12 where the primary handling method for missing data will be the Last Observation Carried Forward (LOCF). For the PP population, number of subjects who were discontinued prematurely due to documented lack of efficacy, worsening condition, or a TEAE is expected to be small. For these subjects the efficacy data from their termination visit will be assigned to the nearest corresponding scheduled visit that has been missed, and carried forward to the subsequent visits for the analysis.

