6.7.3. Change from Baseline

Change from baseline is calculated as (post-baseline result – baseline result). Data will not be imputed for a specific post-baseline time point if the data was not recorded. Changes from baseline will be calculated based on the matched pairs of data points (subjects with data at both baseline and post-baseline).

Percent change from baseline is calculated as (change from baseline/baseline result * 100).

If either the baseline or the post-baseline result is missing, the change from baseline and/or percentage change from baseline will be set to missing.

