Primary Analysis of Efficacy Endpoint Descriptive Statistics of IGA Success[1] Rate at Week 4[2],[3]

ITT Population

		DFD-03 Lotion	Tazorec, 0.1%	Vehicle Lotion	Vehicle Cream,	Total
	Statistics	(n=xxx)	(n=xxx)	(n=xxx)	(n=xxx)	(n=xxx)
Number of Subjects IGA Success at Week 4	n (%)	xx (xx.x)	xx (xx.x)	xx (xx.x)	xx (xx.x)	xx (xx.x)
IGA Score 0 (Clear)	n (%)	xx (xx.x)	xx(xx.x)	xx (xx.x)	xx (xx.x)	xx(xx.x)
IGA Score 0 and at least 2 grade reduction from baseline	n (%)	xx(xx.x)	xx(xx.x)	xx(xx.x)	xx(xx.x)	xx(xx.x)
IGA Score 1 (almost clear)	n (%)	xx(xx.x)	xx(xx.x)	xx(xx.x)	xx(xx.x)	xx(xx.x)
IGA Score 1 and at least 2 grade reduction from baseline	n (%)	xx (xx.x)	xx (xx.x)	xx (xx.x)	xx (xx.x)	xx (xx.x)

^[1] IGA success is defined as an IGA score of 0 (Clear) or 1 (almost clear) with at least a 2-grade reduction from baseline.

Program: T-xxx.sas Programmer: xxx ddmmmyyyy

Programming Notes:

- 1. For table 14.2.3.1.1.3.1, [2] Missing IGA values will be imputed using Multiple Imputation based on Logistic Regression
- 2. For the PP repeat of this table omit footnote [2]

Repeat for:

Table 14.2.1.1.2 Primary Analysis of Efficacy Endpoint Descriptive Statistics of IGA Success Rate at Week 8 – ITT Population

Table 14.2.1.1.3 1 Primary Analysis of Efficacy Endpoint Descriptive Statistics of IGA Success Rate at Week 12 with MI – ITT

Table 14.2.1.1.3 2 Primary Analysis of Efficacy Endpoint Descriptive Statistics of IGA Success Rate at Week 12 ITT Population

Table 14.2.1.1.4 Primary Analysis of Efficacy Endpoint Descriptive Statistics of IGA Success Rate at Week 4 – PP Population.

Table 14.2.1.1.5 Primary Analysis of Efficacy Endpoint Descriptive Statistics of IGA Success Rate at Week 8 – PP Population.

Table 14.2.1.1.6 Primary Analysis of Efficacy Endpoint Descriptive Statistics of IGA Success Rate at Week 12 – PP Population.

^[2] Missing IGA values will be imputed by LOCF.

^[3] Efficacy data from termination visit will be assigned to the nearest corresponding scheduled visit that has been missed and carried forward to the subsequent visits

Table 14.2.1.2.1
Absolute Change from Baseline in Inflammatory and Non-Inflammatory Lesions Counts[1], [2] at the Week 4 Visit ITT Population

		DFD-03	Tazorac, 0.1%	Vehicle	Vehicle	
		Lotion	Cream	Lotion	Cream	Total
	Statistic	(n=xxx)	(n=xxx)	(n=xxx)	(n=xxx)	(n=xxx)
Number of Subjects Evaluated at Week 4 [1]	n (%)	xx (xx.x)	xx (xx.x)	xx (xx.x)	xx (xx.x)	xx (xx.x)

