Count Change Inflammatory Lesion Counts on Face	Mean (SD)	xx(xx.x)	xx(xx.x)	xx(xx.x)	xx(xx.x)	xx(xx.x)
	Median	XX.X	XX.X	XX.X	XX.X	XX.X
	IQR	xx - xx	xx - xx	xx - xx	xx - xx	xx - xx
	Min, Max	XX, XX	XX, XX	XX, XX	XX, XX	XX, XX
Count Change Non-Inflammatory Lesion Counts on Face	Mean (SD)	xx(xx.x)	xx(xx.x)	xx(xx.x)	xx(xx.x)	xx(xx.x)
	Median	XX.X	XX.X	XX.X	XX.X	XX.X
	IQR	xx - xx	xx - xx	xx - xx	xx - xx	xx - xx
	Min, Max	XX, XX	XX, XX	XX, XX	XX, XX	XX, XX
Count Change Inflammatory Lesion Counts on Chest,	Mean (SD)	xx(xx.x)	xx(xx.x)	xx(xx.x)	xx(xx.x)	xx(xx.x)
Back, and Shoulders	Median	XX.X	XX.X	XX.X	XX.X	XX.X
	IQR	xx - xx	xx - xx	xx - xx	xx - xx	xx - xx
	Min, Max	XX, XX	XX, XX	XX, XX	XX, XX	XX, XX
Count Change Non-Inflammatory Lesion Counts on	Mean (SD)	xx(xx.x)	xx(xx.x)	xx(xx.x)	xx(xx.x)	xx(xx.x)
Chest, Back, and Shoulders	Median	XX.X	XX.X	XX.X	XX.X	XX.X
	IQR	xx - xx	xx - xx	xx - xx	xx - xx	xx - xx
	Min, Max	XX, XX	XX, XX	XX, XX	XX, XX	XX, XX

^[1] Missing Lesion counts will be imputed by LOCF.

Program: T-xxx.sas Programmer: xxx ddmmyyyy

Programming Notes:

- 1. For the PP repeat of this table omit footnote [1]
- 2. For table 14.2.1.2.3.1, MI, repeat for each imputation and summary from MIANALYZE

Repeat for:

Table 14.2.1.2.2 Absolute Change from Baseline in Inflammatory and Non-Inflammatory Lesions Counts at the Week 8 visit – ITT Population

Table 14.2.1.2.3 Absolute Change from Baseline in Inflammatory and Non-Inflammatory Lesions Counts at the Week 12 visit – ITT Population

Table 14.2.1.2.3.1 Absolute Change from Baseline in Inflammatory and Non-Inflammatory Lesions Counts at the Week 12 visit with MI-ITT Population

Table 14.2.1.2.4 Absolute Change from Baseline in Inflammatory and Non-Inflammatory Lesions Counts at the Week 4 visit – PP Population

^[2] Efficacy data from termination visit will be assigned to the nearest corresponding scheduled visit that has been missed and carried forward to the subsequent visits.

[name], Ltd Statistical Analysis Plan, Version 1.0 Protocol DFD-03-CD-008 06 Jul 2018

Table 14.2.1.2.5 Absolute Change from Baseline in Inflammatory and Non-Inflammatory Lesions Counts at the Week 8 visit – PP Population Table 14.2.1.2.6 Absolute Change from Baseline in Inflammatory and Non-Inflammatory Lesions Counts at the Week 12 visit – PP Population

Table 14.2.1.3.1

Percent Change from Baseline to Week 4 in Inflammatory and Non-Inflammatory Lesion Counts[1],[2]

ITT Population

		DFD-03	Tazorac, 0.1%	Vehicle	Vehicle	

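### The ITT Week 12 imputation rule does not say how the MI copies are averaged, and the table shells contradict SAP 8.3 on MI and LOCF

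*SAP*

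**What the plan says.** SAP 8.3 plans three layers of efficacy summary.

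- **Unimputed, ITT and PP:** "data will be summarized at week 4, 8 and 12 with data as is where missing data is not imputed".
- **ITT Week 12 with MI:** missing IGA and lesion counts are imputed by regression. Then: "The average score of the MI copies will be used to calculate the summary statistics". Protocol 11.4 has the same sentence.
- **PP Week 12 with LOCF:** IGA, lesion counts and CADI.

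SAP 8.1.1 describes the scale: "IGA is an ordinal scale with five severity grades (reported only in integers, e.g., 0 to 4". Success is grade 0 or 1 together with a fall of at least two grades.

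Other parts of the SAP also give imputation rules.

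- **6.8.1:** "Missing efficacy endpoints will be imputed for week 12 IGA and lesion count analyses only". It refers to 8.3 for details.
- **6.7.3:** "Data will not be imputed for a specific post-baseline time point if the data was not recorded".
- **IGA shell (Table 14.2.1.1.1, ITT Week 4, and its repeats):** the footnote reads "Missing IGA values will be imputed by LOCF". A programming note for the MI version reads "Missing IGA values will be imputed using Multiple Imputation based on Logistic Regression". Another note drops the LOCF footnote for the PP repeats.
- **Lesion shells (Tables 14.2.1.2.1 and 14.2.1.3.1, ITT):** the same pattern, with an LOCF footnote that is dropped for PP. For the MI version of absolute change: "For table 14.2.1.2.3.1, MI, repeat for each imputation and summary from MIANALYZE".
- **ITT shells for IGA, lesion counts and CADI:** a further footnote carries termination-visit data forward to later visits.

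**The concern.** MI normally means analysing each completed dataset and then combining the results. Averaging the copies within a subject first turns MI into a single imputation by a near-expected value. That has two consequences here. A responder definition applied to an averaged grade estimates a different quantity from the average of the responder indicator, and a fractional grade fits neither the definition nor the shell rows for grades 0 and 1. The spread of lesion change is also understated, because the residual variation in imputed values is mostly averaged away.

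The shells do not settle the matter, because they describe other procedures. Two competent programmers, one following 8.3 and one following the shells, would produce different efficacy tables, and the choice could be made after unblinding. If missingness differs between arms, the per-subject method also creates a difference in success where none exists.

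**Working it through.** The documents give no MI result, number of copies or expected success rate, so there is no figure of the plan's own to reproduce.

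**Inputs from the documents.** About 150 randomised and 120 completers, so planned non-completion is 30/150 = 20%. Each active arm has 50 subjects. The 20% is an upper figure for missing Week 12 data, because protocol 7.7 asks for the Week 12 evaluations at withdrawal where possible and protocol 11.4 assigns withdrawal data to the nearest missed visit.

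**Assumptions.** True success p = 10, 25 or 40%. R² of Week 12 on earlier data = 0.2, 0.5 or 0.8. M = 20 copies. Data missing at random, with imputations drawn from the true model. Model A: a latent normal cut so that P(grade 0) = 0.25p and P(grade ≤ 1) = p, with the rest split 45/45/10 over grades 2, 3 and 4.

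**IGA success.** With missing fraction m, the reported rate is (1 − m)p + m·q, where q is the share of imputed subjects classed as successes. Deriving success within each copy gives q = p and no bias. Averaging first gives, at m = 20%, this bias in points:

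| p | Average ≤ 1 (R² 0.2 / 0.5 / 0.8) | Rounded (R² 0.2 / 0.5 / 0.8) |
|---|---|---|
| 10% | −2.0 / −1.7 / −1.2 | −1.8 / −0.9 / −0.4 |
| 25% | −4.8 / −3.7 / −2.7 | −3.4 / −1.6 / −0.6 |
| 40% | −7.1 / −5.2 / −3.9 | −3.6 / −1.8 / −0.7 |

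Model B (latent grade cut at 0.5, 1.5, 2.5 and 3.5; SD 0.8 to 1.2; up to 20% of subjects at baseline grade 2) gives −1.4 to −7.2 and −0.3 to −3.6. Over both models the range is 1.2 to 7.2 points (≤ 1) and 0.3 to 3.6 points (rounded). The bias is proportional to m, so 10% missing halves it and 5% quarters it.

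**Worked example.** Model A with p = 25% and R² = 0.5 gives q = 6.3% (≤ 1) or 17.1% (rounded).

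- 20% missing: 0.8 × 25 + 0.2 × 6.3 = 21.3%. Rounded: 20 + 0.2 × 17.1 = 23.4%. Per copy: 25.0%.
- 10% missing: 22.5 + 0.1 × 6.3 = 23.1%. Rounded: 22.5 + 0.1 × 17.1 = 24.2%.
- 10% missing in one arm and 20% in the other, equal true success: a spurious difference of (25 − 6.3) × 0.10 = 1.9 points, or (25 − 17.1) × 0.10 = 0.8 points rounded.
- For scale, in an arm of 50 one subject is 2 points and the binomial SE is √(0.25 × 0.75/50) = 6.1 points.

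**Sensitivity.**

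- With M = 5, Model A gives 1.1 to 5.7 points (≤ 1) and 0.2 to 2.4 points (rounded) at 20% missing.
- If earlier data predict nothing (R² = 0), M = 20 and other assumed grade distributions, true rates of 20% and 35% are reported as 16.0% and 28.0% (≤ 1), or 16.0% and 28.5% (rounded).
- At 60 to 70% success the rounded bias runs from −2.1 to +2.8 points by model, so its sign is not fixed outside the 10 to 40% range.
- The share of imputed subjects with a fractional average is about 95% with 20 copies and about 67 to 82% with five.

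**Lesion-change SD.** The ratio of the averaged SD to the per-copy SD is √[(1 − m) + m(R² + (1 − R²)/M)]. At m = 0.20, M = 20:

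- R² = 0.2: √(0.80 + 0.20 × 0.240) = 0.921
- R² = 0.5: √(0.80 + 0.20 × 0.525) = 0.951
- R² = 0.8: √(0.80 + 0.20 × 0.810) = 0.981

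At 10% missing the ratios are 0.961 to 0.990. The mean does not change.

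**Passages side by side.**

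| Item | SAP 8.3 | Elsewhere in the SAP |
|---|---|---|
| Combining copies, lesion change | Average the copies, then summarise | Shell: summarise each imputation, then MIANALYZE |
| IGA imputation | Regression | Shell: logistic regression; silent on where success is derived |
| ITT Weeks 4, 8 and 12, unimputed tables | No imputation | Shells: LOCF footnotes on IGA, lesion counts and percent change |
| PP Week 12 | LOCF | Shells: omit the LOCF footnote for PP |
| CADI, PP Week 12 | LOCF | 6.8.1: imputation for IGA and lesion counts only |

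**The case against.** The sentence in 8.3 does not say that averaging is per subject. It can be read as averaging results across copies, and the SAP's one specific instruction on combining copies, the MIANALYZE note, points that way. The logistic note suggests categorical grades within each copy. This stands: the bias figures apply only on the per-subject reading, and it would go too far to say that the plan definitely prescribes a biased estimator. What remains is that the text does not choose between the readings, and the MIANALYZE note covers only absolute lesion change.

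Several shell pages carry Version 1.0 or July 2018 headers inside a Version 2.0 SAP of September 2018, so the LOCF footnotes may be carry-over. SAP 6.4 also describes the shells as expected layout. That may explain the conflict, but 6.4 makes the shells part of the SAP and nothing says that 8.3 overrides them.

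A reader might infer that 6.7.3 forbids the MI outright. It does not: 6.8.1 states the Week 12 exception and refers to 8.3, so a cross-reference is enough. The missing MI table for percent change and the single PP Week 12 table per endpoint are gaps in the table list. As-is and LOCF results in PP should nearly coincide, because few PP subjects lack Week 12 data.

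The effect is also small. In the worked example it is below one standard error, and at 5% missing it is at most 1.8 points.

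**Conclusion.** The point holds as an ambiguity with a real contradiction behind it. On the natural reading of 8.3, the ITT Week 12 MI success rate is 1.2 to 7.2 points too low (average ≤ 1) or 0.3 to 3.6 points too low (rounded), and the lesion-change SD is 2 to 8% too small. These figures rest on 20% missing, M = 20, success of 10 to 40%, R² of 0.2 to 0.8 and data missing at random. All are assumptions except the 20%, which is planned non-completion used as an upper figure. The conflicts over LOCF on ITT, LOCF on PP and CADI do not depend on those assumptions.

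A reader might infer that the trial's conclusions are at risk. The documents do not support that. Efficacy is secondary and descriptive, the study is not powered, safety data are not imputed, and unimputed ITT Week 12 tables are also listed. The change should be made because it is cheap and removes a choice that could otherwise be made with the data in view.

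**What to change.** Replace the averaging sentence in SAP 8.3, and record the departure from protocol 11.4, with wording such as: IGA is imputed as integer grades by ordinal logistic regression; IGA success and lesion change are derived within each imputed dataset; the success percentage and the mean are computed per dataset and pooled; SD, median and quartiles are computed per dataset and averaged; the number of imputations is [to be stated]. Say also what the minimum and maximum in the MI table refer to.

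Then align the rest.

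- Limit the MIANALYZE note to the pooled proportion and mean, and apply it to both MI tables.
- Remove the LOCF and carry-forward footnotes from the unimputed ITT tables, including CADI. Protocol 11.4's assignment of termination data to the nearest missed visit can stay.
- Put an MI footnote on the Week 12 MI tables.
- Replace the notes that omit the LOCF footnote for PP, so that it appears on the PP Week 12 LOCF tables and not on the unimputed PP tables.
- Add CADI (PP) to 6.8.1.
- Housekeeping: a cross-reference from 6.7.3 to 6.8.1 and 8.3; table-list entries for the PP LOCF tables, and for MI percent change or a statement that none is planned; and the table number in the IGA MI note, which does not match the index.

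The cost is a few sentences and footnotes. The procedure is one the lesion shell already names, and no new data are needed.
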